3. DESCRIPTION OF DESIGN AND TRIAL POPULATION

3.1 OVERALL TRIAL DESIGN AND PLAN

This is a single arm, open label, phase Ib dose escalation study. Approximately 20 relapsed/refractory CLL patients who have been pre-treated with at least one prior line of systemic treatment and who qualify for treatment with ibrutinib will be treated with a combination of BI 836826 and ibrutinib in this trial.

Ibrutinib is to be dosed at a fixed, approved dose of 420mg daily in all patients. Stepwise dose escalation of BI 836826 will be performed. BI 836826 will be administered on cycle 1 on following days: D1 (10mg), D2 and D8 (50% of the assigned dose on each day), D15 (100% dose). In C2-4 BI 836826 will be administered on days: 1 and 15 of each cycle at 100% of the assigned dose.

Dose-escalation of BI 836826 will be guided by a BLRM with overdose control (refer to [Section 7](#)). The BLRM estimates the MTD by updating estimates of the probability of observing a DLT in the first cycle for each dose level in the study as patient information becomes available. At any time in the trial, it will not be permitted to escalate to a dose which does not fulfil the Escalation With Overdose Control (EWOC) criterion (refer to Section 7). Dose-increments will be $\leq 100\%$ of the previous dose level tested in prior cohort.

For any dose-escalation cohort, at least 3 patients will be required (Section 7). However, in the case that only 2 patients are evaluable and neither has experienced a dose-limiting toxicity within the first cycle (28 days) of the combination treatment, then dose-escalation can occur based on these 2 patients.

A patient will be considered evaluable for DLT in cycle 1 (D1 to D28 of combination treatment)

- if the patient has been observed for at least one cycle and has had sufficient exposure to both study drugs, i.e. 4 infusions of BI 836826 (10 mg, 50% of target dose x 2, and 100% of target dose x1) and $\geq 80\%$ (22 of 28 doses) of ibrutinib doses.
- if the patient has experienced a DLT independent of exposure time in cycle 1.

Patients who do not meet at least one of the above criteria will be considered for the safety analysis, but will be replaced by an additional patient for DLT assessment.

After all patients in a cohort have either experienced a DLT or have been observed for at least one cycle (28 days) without experiencing a DLT, the Bayesian model will be updated with the newly accumulated data. The overdose risk will then be calculated for each dose, and escalation will be permitted to all doses which fulfil the EWOC criterion and the additional 100% escalation rule

If DLTs are observed in the first two consecutive patients of a previously untested dose level, subsequent enrollment to that cohort will be stopped. The BLRM will be re-run to confirm that the dose-level still fulfils the EWOC criterion. Based on this information, the SRC will

evaluate whether the next patients will be enrolled on the same dose level, or if they will be enrolled to a lower dose level.

Based on the model and on additional information, if available (PK, PD, patient profiles), the members of the SRC will reach a joint decision on the next dose level to be investigated. The SRC may also provide a recommendation for the size for the next dose cohort. However, the final decision on the next cohort size will be agreed mutually between the Sponsor and the CI.

The SRC may recommend stopping the dose finding phase after the criterion for MTD (see [Section 7.1](#)) is fulfilled. Further patients may be included to confirm this MTD estimate.

If a MTD is determined during dose escalation, the RP2D may be either the MTD or a lower dose. If no MTD is observed after escalation to the highest possible dose of 1400 mg, 1400mg or a dose below 1400 mg may be selected as RP2D. The RP2D will be a safe dose at which the intended clinical efficacy (e.g. one or more of the following are observed: ALC lowering effect, clinical CR, MRD negativity, effect on biomarkers). A minimum of 6 patients need to be evaluated at the RP2D..

During dose escalation, enrollment into the first dose cohort will be allowed only after the first patient in the cohort is evaluable for safety for a minimum of 3 days from the first administration (10 mg pre-dose) of BI 836826. Subsequent patients within this cohort and subsequent cohorts may be enrolled at any time.

Enrollment into the next higher dose cohort is allowed after the previous dose cohort is found to be safe for all patients in this cohort by the SRC. For the purposes of determining dose escalation, DLTs will be assessed based on safety data from cycle 1. However, AEs including those qualifying for DLT will be monitored beyond cycle 1 and throughout the trial.

Treatment:

Ibrutinib is going to be dosed at fixed, approved dose of 420mg daily in all patients. Stepwise dose escalation of BI 836826 will be performed. BI 836826 will be administered in Cycle 1 on the following days: D1 (10mg), D2 and D8 (50% of the assigned dose on each day), D15 (100% of the assigned dose). In Cycle 2-4 BI 836826 will be administered at the assigned dose on days 1 and 15 of each cycle. In Cycle 5-12 BI 836826 will be administered at the assigned dose on day 1 only. Patients will continue the study treatment till disease progression, unacceptable toxicity, or withdrawal of consent. Continued monthly treatments beyond cycle 12 are possible for patients with a CR, CRi, or MRD negative PR in the response assessment at the end of Cycle 12. In such cases, patients may continue treatment with 12 additional cycles of combination treatment up to a maximum and total of 24 treatment cycles.

Patients will take two weeks of ibrutinib during the run-in phase, prior to start of BI 836826 and will continue ibrutinib throughout the whole duration of the study. After completion of the study the continued treatment with ibrutinib is left to the decision of the investigator or patient's physician, depending on patients' disease status, and the need for further treatment.

For selection of doses please refer to [Section 4.1.3](#).

For dose adaptation in case of AEs please refer to [Section 4.1.4.5](#).

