Each patient enrolled, completing the screening period and meeting eligibility will enter the run-in phase and start with ibrutinib monotherapy pre-treatment on Day -14 through Day -1. While AEs from this period will be collected, they will not constitute part of the DLT evaluation period for combination therapy. The dose for ibrutinib will be 420mg daily, orally.

Cycle 1:

Patients completing the screening period and run-in phase will start the combination treatment. For prevention of IRRs and tumor lysis syndrome the first administration of BI 836826 will be a pre-dose of 10 mg/ml on Day 1. Subsequent two doses will be 50% of the target dose on Day 2 and on Day 8, followed by 100% of the target dose on Day 15 of the first cycle. Patients will continue to receive ibrutinib on days 1-28 of cycle 1. DLTs from the start of the first BI 836826 infusion through the MTD evaluation period (Cycle 1) as well as other AEs will be used to assess dose escalation steps and to determine the MTD.

Cycle 2-4:

Patients will receive 100% of assigned dose of BI 836826 on days 1 and 15 of each cycle. Patients will continue to receive ibrutinib on days 1-28 of each cycle (2-4). At the end of Cycle 3 (Imaging and Laboratory) and Cycle 4 (Laboratory) disease assessment will be performed. Patients without disease progression of CLL will be allowed to continue with BI 836826 and ibrutinib.

Cycle 5-12:

Patients will receive 100% of assigned dose of BI 836826 on Day 1 of each cycle. Patients will continue to receive ibrutinib on days 1-28 of each cycle. Disease assessment will be performed every three cycles or 12 weeks, and will be performed at the end of every third cycle, i.e. Day 21 through Day 28 of Cycle 6, 9, and 12. Treatment with BI 836826 will be terminated at the end of cycle 12 in all patients who achieve PR (MRD positive), PR-L, Stable Disease (SD) or PD in the response assessment at the end of cycle 12. Patients who achieve a CR (MRD positive or negative) or a PR (MRD negative), may continue treatment with BI 836826 as outlined below for additional 12 cycles. Treatment with ibrutinib monotherapy may be continued according to label at the discretion of the investigator or the patient's physician.

Cycle 13-24 (patients with CR and MRD-negative PR only):

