5.3.6.2 Dose limiting toxicities

All drug related AEs, including SAEs and deaths, will be carefully evaluated by investigators for DLT. Dose escalation decisions will be based on DLTs observed in Cycle 1. Dose Limiting Toxicity is defined as follows:

- Any non-hematologic AE of Grade ≥ 3 related to BI 836826 and/or ibrutinib will be considered DLT, except:
 - Infusion-related reaction, any Grade
 - Grade 3 AST- and/or ALT elevation without concomitant bilirubin elevation or any other asymptomatic Grade 3 laboratory abnormality with spontaneous recovery within 1 week
- The following hematologic AEs related to BI 836826 and/or ibrutinib will be considered DLT:
 - Grade 4 neutropenia with concomitant infection
 - Grade 4 febrile neutropenia, and Grade 3 febrile neutropenia not resolving within 72 hours with appropriate treatment (antibiotics, antivirals, antifungals, growth factor support)
 - Grade 4 thrombocytopenia with clinically significant bleeding
 - Grade 4 anemia
 - Any Grade 5 hematologic AE

Patients will be evaluable for MTD in Cycle 1 if:

- a DLT occurs at any time, or
- a minimum exposure to BI 836826 and ibrutinib has been achieved. The minimum exposure is defined as $\geq 80\%$ of the planned ibrutinib doses (since Day 1 of Cycle 1) and all planned administrations of BI 836826 in Cycle 1. If the administration in Cycle 1 on Day 15 is delayed, the DLT evaluation will be prolonged to cover 14 days after the D15 administration.

All patients who have started trial treatment, but do not meet at least one of the above criteria at the end of Cycle 1 will be evaluated for safety, but replaced for MTD evaluation.

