Demographics (sex, birth date, race and ethnicity) will be collected during the screening visit. A detailed cancer history will be obtained. The date of first diagnosis of CLL (month and year may be sufficient) will be recorded in the eCRF. The current stage according to the Rai classification (See [Section 10.1](#)) should be recorded [[R10-4429](#)]. Previously administered chemo- and immunotherapy will be documented, including start and end dates (year and month may be sufficient), the treatment regimen/protocol with the number of courses (chemo-, immunotherapy), the best response obtained (CR, Cri, PR, PR-L, SD, PD, unknown). If the patient has received an autologous Stem Cell Transplant (SCT) or an allogeneic stem cell transplant, procedural details, including the treatment regimen prior to transplantation should be collected. Documentation of previous radiotherapy should include the total radiation dose and radiation field(s). Previous surgeries within the past 5 years should be recorded. In addition, any previous surgery, which may, according to the investigator affect tumor assessment in this trial, e.g. splenectomy or removal of lymph nodes, should be documented in the eCRF.

Re-screening:

Sites will be allowed to re-screen patients. If more than 3 weeks have elapsed prior to re-screening, all screening procedures must be repeated. In case a patient is re-screened, the patient will keep the same assigned patient number.

Below are the specific requirements during the screening period. For a global overview of tests to be performed, please refer to the [Flow Chart](#).

Run-In Phase:

Patients who complete the screening phase and are still eligible will enter the run-in phase. The run-in phase will begin with the first dose of ibrutinib and continue for two weeks of dosing (+/- 2 days) until Cycle 1 Day 1. Patients who are unable to receive $\geq 80\%$ of ibrutinib doses (12 doses) during the run-in phase will be ineligible to continue on trial and would be considered "screen failures". These patients do not need to continue on trial nor complete an EOT Visit or follow-up. They will need to be replaced. To confirm compliance with daily dosing of ibrutinib during the run-in phase and Cycle 1, patients entered in the trial will be required to maintain and complete a dosing diary. At the end of the run-in phase and prior to the first infusion of BI 836826 on day 1, patients must meet the laboratory requirements listed in [Section 4.1.4](#).

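### Protocol Section 3.1 equates at least 80% ibrutinib exposure with 22 of 28 doses, but 22/28 is 78.6%; the evaluability of a DLT-free patient with exactly 22 doses is undetermined

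*Protocol*

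**What the plan says.** Protocol Section 3.1 opens the rule with "A patient will be considered evaluable for DLT in cycle 1 (D1 to D28 of combination treatment". Without a DLT, the patient needs all four BI 836826 infusions and at least 80% of ibrutinib doses, with the bracketed equivalent "22 of 28 doses) of ibrutinib doses". The other route to evaluability is "if the patient has experienced a DLT independent of exposure time in cycle 1". A patient who meets neither condition stays in the safety analysis "but will be replaced by an additional patient for DLT assessment".

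Protocol Section 5.3.6.2 states the rule again without a count: at least 80% "of the planned ibrutinib doses (since Day 1 of Cycle 1) and all planned administrations of BI 836826 in Cycle 1". Its other route is "a DLT occurs at any time, or". It adds that the DLT window is prolonged if the Day 15 infusion is delayed.

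Protocol Section 4.1.4 fixes the denominator: "Patients will continue to receive ibrutinib on days 1-28 of cycle 1".

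SAP Section 6.3 sets no exposure cut-off. Its MTD evaluation set is the treated patients who were not replaced. It refers to Protocol Section 3.3.4.1 for the replacement rules and takes the list of replaced patients from the Trial Clinical Monitor.

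**The concern.** The cut-off decides whether a DLT-free patient counts in the DLT denominator and in the Bayesian logistic regression model (BLRM), or is replaced. Here the percentage and the count give opposite answers for a patient with 22 doses.

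The ambiguity works in one direction. A patient with a DLT is evaluable whatever the exposure, so the looser count can only bring in patients who contribute zero DLTs. Each one lowers the posterior probability of overdosing. With cohorts of about three, one patient can matter when that probability lies close to the 0.25 limit.

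The SAP offers no tie-breaker. The section it cites, Protocol 3.3.4.1, covers removal of patients from treatment and contains no replacement rule. The replacement criteria stand only in Protocol Sections 3.1 and 5.3.6.2, the two places that disagree.

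**Working it through.** **Inputs.** Threshold of at least 80% (Protocol 3.1 and 5.3.6.2); printed count 22 of 28 (3.1); 28 planned daily doses in Cycle 1 (4.1.4).

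**Where 22 comes from.** 0.80 × 28 = 22.4. Rounding down, or to the nearest whole number, gives the printed 22. A minimum has to be rounded up:

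- 22/28 = 0.786, below 0.80. Rounded to a whole percent it is 79%, still short.
- 23/28 = 0.821, the first count that passes.

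**Who is affected** (28 planned doses, no DLT, all Cycle 1 infusions given):

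| Ibrutinib doses | By the count in 3.1 | By the percentage in 3.1 and 5.3.6.2 |
|---|---|---|
| 21 or fewer | not evaluable | not evaluable |
| 22 | evaluable | not evaluable |
| 23 or more | evaluable | evaluable |

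**Illustration of what one patient can do.** Table 10.7:1 scenario 5 has 0/3 DLTs at 100 mg and 0/3 at 200 mg. It prints P(overdose) at 400 mg as 0.248, against the limit of 0.25 in Protocol 7.1. The model was re-run with the Table 7.1:3 prior by weighting simulated prior draws with the binomial likelihood.

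The interaction term needs an assumption. As printed in Protocol 7.1 it contains log(d2/d2*). At 420 mg ibrutinib this is log(420/420) = 0, so the printed term drops out. Replacing it by η × (d1/200) gives prior P(overdose) at 50/100/200/300/400 mg of 0.098/0.132/0.242/0.374/0.464. Table 7.1:4 prints 0.096/0.131/0.241/0.373/0.463. That form is therefore used, with no interaction as a sensitivity check.

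| Data (100 mg; 200 mg) | P(overdose) at 400 mg, η × (d1/200) | No interaction |
|---|---|---|
| 0/3; 0/3 | 0.241 | 0.227 |
| 0/3; 0/2 (one 200 mg patient dropped) | 0.274 | 0.254 |
| 0/2; 0/3 (one 100 mg patient dropped) | 0.252 | 0.238 |

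The re-run gives 0.241 where the protocol prints 0.248, a difference of 0.007. Dropping a 200 mg patient adds 0.274 − 0.241 = 0.033 (0.254 − 0.227 = 0.027 with no interaction) and crosses 0.25 in both forms. Dropping a 100 mg patient exceeds the limit by only 0.002 in one form and not at all in the other, so no conclusion rests on that row.

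**The case against.** The strongest reply is that the percentage is the rule and the count is only a gloss. Both sections say at least 80%, so a careful reader would apply 80% and treat 22 as a rounding slip. This limits the point to one exposure value but does not remove it: a site or monitor working from Section 3.1 would naturally use the printed count.

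The illustration is also a selected case. It is the printed scenario closest to the limit, and it assumes that the patient is not replaced. Both sections call for replacement, and a DLT-free replacement restores 0/3 and 0.241. The Safety Review Committee (SRC) also weighs other information besides the model. All of this stands, so the figures show what one patient can do, not an expected effect.

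Version 2.0 stops recruitment, and its amendment description says that the trial is being stopped before the MTD is reached. What remains is a descriptive DLT table and posterior probabilities in an abbreviated report. This lowers the severity. Nor does the SAP re-apply the cut-off when the set is built; it uses the replacement list. Re-deriving the set from dosing records could therefore leave the report out of step with the data the SRC used.

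A reader might infer two further defects that the documents do not support:

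- **Run-in count.** Protocol 6.2.1 says that patients without at least 80% "of ibrutinib doses (12 doses) during the run-in phase will be ineligible to continue on trial". For the stated 14 days, 0.80 × 14 = 11.2, which rounds up to 12 (12/14 = 85.7%), so that count is right. It is nominal when the run-in varies by 2 days either way (12/16 = 75%), and it does not govern DLT evaluability.
- **Prolonged window.** A count of 22 would be far too low over 35 days (22/35 = 62.9%). But Section 3.1 ties its count to Days 1 to 28, and the percentage in Section 5.3.6.2, where the extension is defined, scales with the planned doses. Nothing applies 22 to a longer window.

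**Conclusion.** The error is exact and needs no assumption: 22 of 28 is 78.6%, and at least 80% requires 23. Section 3.1 contradicts itself and Section 5.3.6.2, and SAP Section 6.3 does not settle the matter because its cross-reference leads to a section without a replacement rule.

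The reach is narrow. In a 28-day window it concerns only a DLT-free patient with all Cycle 1 infusions and exactly 22 doses. The documents do not show whether one exists. The direction is known: the looser count can only lower the estimated overdose risk.

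The size in the model, 0.241 to about 0.274 at 400 mg in scenario 5, rests on the assumed interaction form and on an unreplaced patient at 200 mg. It would be wrong to infer that an escalation decision in this trial was reversed, or probably would be. This should be fixed, because the threshold feeds a primary endpoint and the correction is one number.

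**What to change.** 1. Reconcile Protocol Sections 3.1 and 5.3.6.2 so that count and percentage agree. If at least 80% is the intended rule, the count is at least 23 of 28. Alternatively, delete the count and keep at least 80% of the planned doses in the DLT window actually observed.
2. In SAP Section 6.3, point the replacement rule to Protocol Sections 3.1 and 5.3.6.2 instead of 3.3.4.1.
3. Before database lock, check the Cycle 1 dosing records for any DLT-free patient with all infusions and exactly 22 ibrutinib doses, and record the result. If there is one, keep the set the SRC used and report the DLT table and MTD analysis with and without that patient.

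The cost is two wording changes and one check of data already collected, plus one repeat model run if such a patient is found. With recruitment stopped, a patient left out in that repeat run cannot be replaced, so the two results should be shown side by side.

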Tumor Lysis Syndrome:

In patients with a high tumor burden who are exposed to a highly effective therapy, there is a risk of rapid tumor destruction resulting in Tumor Lysis Syndrome (TLS). Prophylaxis, close monitoring and appropriate interventions are the key to preventing and managing TLS. Instructions and reference to published guidelines on TLS are included in this protocol as a prophylactic measure (see [Section 4.2.1.2.2](#)).

Drug-Drug Interaction (DDI) potential of ibrutinib:

Ibrutinib is metabolized to a great extent by 3A enzyme of p450 complex. Strong CYP3A inhibitors have been demonstrated to increase C_{max} and AUC of ibrutinib by 29- and 24-fold. Patients and investigators will be advised to avoid strong and moderate CYP3A inhibitors.

Drug induced liver toxicity:

Although rare, a potential for drug-induced liver injury is under constant surveillance by sponsors and regulators. Therefore, this trial requires timely detection, evaluation, and follow-up of laboratory alterations in selected liver laboratory parameters to ensure patients' safety, see also [Section 5.3.6.1](#).

Ongoing safety analysis:

An ongoing safety evaluation will be performed by a SRC composed of members from the sponsor together with the Coordinating Investigator (CI) and participating investigators in regular intervals after completion of MTD observation period (Cycle 1) for all patients in each dose escalation cohort.

Overall the risk benefit is considered positive for the combination of BI 836826 and ibrutinib. Moreover, if proven safe, this combination has the potential to improve the CR rate compared to historical data for ibrutinib alone, and to introduce treatment free intervals, which in turn might prevent development of drug resistance in CLL patients. Considering the chronic

nature of CLL and the need for repeated treatment, this potential benefit of therapy with BI 836826 in combination with ibrutinib is expected to outweigh the treatment-related risks.

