In case BI 836826 is discontinued permanently for reasons other than PD, at any other timepoint than end of cycle 12 or end of cycle 24, e.g. due to AEs, the patient should complete an EOT visit as soon as possible after discontinuation of BI 836826 or when the decision to discontinue BI 836826 is taken.

If the EOT is performed less than 30 days after the last dose of BI 836826, an additional EoR visit has to be scheduled after 30(+ 7 days), if the EOT visit is ≥ 30 days after the last dose of BI 836826, the EOT and EoR may be performed on the same date.

The "last-patient-last-visit-primary-endpoint" is defined in [Section 8.6](#).

All patients should adhere to the visit schedule as specified in the [Flow Chart](#). However, in case a patient misses a visit and the patient reports to the investigator between the missed and the next scheduled visit, the procedures that were planned at the missed visit should be done and the actual date and the reason for the delay should be documented in the eCRF. In the case a Day 1 treatment of BI 836826 is delayed, all subsequent visits of a cycle will be recalculated based on the actual date of Visit 1 of the delayed cycle. Some flexibility is allowed in scheduling the visits according to the time window specified in the Flow Chart.

If pathological laboratory values or other issues require an additional unscheduled visit, new eCRF pages will be completed for the unscheduled visit. At the unscheduled visit, it is sufficient to record only the clinical relevant labs/examinations performed.

In case ibrutinib is to be discontinued permanently for other reasons than PD, patients may be kept on BI 836826 and follow the treatment visit schedule as outlined in the Flow chart.

Treatment may be delayed to enable resolution of AEs, concurrent diseases or recovery from surgical procedures, or other individual reasons. Day 15 in Cycles 1-4 may be delayed by 1 week, in case a longer delay would be required, this dose should be omitted. Day 1 in Cycles 2-24 may be delayed by up to 4 weeks. In case longer delays would be required, this should be discussed and agreed between the investigator and the sponsor's Clinical Monitor. Ibrutinib dose modifications will be at the discretion of the Investigator. Changes in ibrutinib dosing will be recorded in the eCRF.

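### Protocol Section 3.1 permits the BLRM update after 28 DLT-free days, although Section 5.3.6.2 and the SAP keep the DLT window open until 14 days after a delayed Day 15 dose

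*Protocol*

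**What the plan says.** **The 28-day clock.** Protocol Section 3.1 states that when every patient in a cohort has had a DLT "or have been observed for at least one cycle (28 days) without experiencing a DLT, the Bayesian model will be updated". It defines evaluability over Day 1 to Day 28 of combination treatment, and its first criterion applies "if the patient has been observed for at least one cycle and has had sufficient exposure to both study drugs", meaning all four Cycle 1 infusions and enough ibrutinib. The rule allowing escalation on two evaluable patients also refers to a 28-day first cycle. Section 2.3 places the safety review "after completion of MTD observation period (Cycle 1) for all patients in each dose escalation cohort", which equates the observation period with Cycle 1.

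**The clock tied to the dose.** Section 5.3.6.2 says that if the Cycle 1 Day 15 infusion is late, "the DLT evaluation will be prolonged to cover 14 days after the D15 administration". SAP 5.1 builds this into the primary endpoint: the MTD evaluation period runs from the first BI 836826 administration to 14 days after the Day 15 administration.

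**The permitted delay.** Section 6.1 says "Day 15 in Cycles 1-4 may be delayed by 1 week", so the first full dose can fall as late as Day 22.

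Section 3.1 neither mentions the prolongation nor refers to Section 5.3.6.2.

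**The concern.** The two clocks agree when the Day 15 dose is given on time and separate when it is late. The prolongation in Section 5.3.6.2 gives 14 days of observation after the first 100% dose. Section 3.1 can be satisfied before those days have passed.

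The model in Section 7.1 has a binomial likelihood: each patient enters as a DLT or a non-DLT, with no partial credit for incomplete follow-up. A patient entered on Day 28 with the window still open counts as a full non-DLT. If a DLT then occurs, the posterior used for that escalation decision was too favourable, and the next cohort may have been released at a dose the complete data would not have allowed. Under the two-patient rule, one such patient is half of the cohort's data.

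**Working it through.** **Step 1: day arithmetic.** Inputs: Day 15 dose delayed by 0 to 7 days (Section 6.1), window end 14 days after the actual dose (Section 5.3.6.2, SAP 5.1), earliest update Day 28 (Section 3.1).

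Window end = (15 + delay) + 14, or one day earlier if the dose day counts as day 1 of the 14. Days elapsed since the full dose on Day 28 = 28 − (15 + delay) = 13 − delay.

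| Full dose given | Window ends | Days since dose on Day 28 | Window days after Day 28 |
|---|---|---|---|
| Day 15 | Day 28–29 | 13 | 0–1 |
| Day 18 | Day 31–32 | 10 | 3–4 |
| Day 22 | Day 35–36 | 6 | 7–8 |

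With no delay the rules agree to within a day. At the longest delay the gap is 7 to 8 days.

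**Step 2: when a patient is still unfinished at the update.** The trigger applies to the whole cohort. When the last patient reaches Day 28, a patient who started k days earlier is on Day 28 + k. A patient dosed on Day 22 has passed Day 36 if k is at least 8. The problem therefore needs a delayed Day 15 dose and a patient who started within about a week of the last one, or is the last one.

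**Step 3: reproduce the protocol's model.** Inputs: mixture priors from Table 7.1:3, reference doses 200 mg and 420 mg, and the requirement that P(DLT rate ≥ 0.33) be below 0.25 (Section 7.1). I drew 1.5 million parameter sets from the prior and weighted each by the product over doses of p^r(1 − p)^(n − r). P(overdosing) is the weighted share with p ≥ 0.33.

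The interaction printed in Section 7.1 multiplies two logarithms. At 420 mg ibrutinib it vanishes, because log(420/420) = 0. An interaction on the product of the dose ratios reproduces the protocol's tables more closely, so both are shown.

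| Data | Dose | Protocol | Ratio form | Printed log form |
|---|---|---|---|---|
| Prior | 100 mg | 0.131 | 0.133 | 0.125 |
| Prior | 200 mg | 0.241 | 0.243 | 0.209 |
| Prior | 400 mg | 0.463 | 0.465 | 0.434 |
| 0/3 at 100, 0/3 at 200 (scenario 5) | 400 mg | 0.248 | 0.242 | 0.228 |
| 0/3 at 100, 1/3 at 200 (scenario 6) | 200 mg | 0.163 | 0.162 | 0.126 |

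Scenario 6 prints two overdose probabilities for 200 mg, 0.208 as current dose and 0.163 as next dose. The recalculation matches the second. Both are below 0.25, so the decision is unaffected.

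**Step 4: effect of one DLT in the gap.** Suppose the 200 mg cohort is entered as 0/3 but is 1/3 once the window closes.

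- P(overdosing) at 400 mg rises from 0.242 to 0.486 (log form: 0.228 to 0.422).
- P(overdosing) at 300 mg becomes 0.362 (log form: 0.292).
- Both doses then fail the 0.25 limit, and 200 mg passes.

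This agrees with Table 10.7:1: scenario 5 permits 400 mg, and scenario 6 stays at 200 mg.

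**The case against.** - **Twenty-eight days is a floor.** The wording is at least one cycle, and Section 5.3.6.2 is the more specific rule on DLTs. This stands: Section 3.1 permits the early update and does not require it. But nothing in Section 3.1 makes the patient pending.
- **The SAP already uses the right period.** SAP Section 3 describes the BLRM in terms of DLTs in the MTD evaluation period, and SAP 7.4 uses that period for estimation. This protects the final analysis. It does not set the time of an interim update, which is governed by protocol Sections 3.1 and 2.3.
- **Cycle 1 might be read as lengthening with the delay.** No text says so. The flow chart plans 28-day cycles with the next starting on Day 29, and Section 6.1 recalculates visits only when a Day 1 treatment is late. Section 4.1.4, like Section 2.3, equates the MTD period with Cycle 1.
- **The SRC sees individual profiles and later adverse events, and has a charter.** A late infusion would probably be noticed, and the charter, which is not among the documents, may cover it. But the overdose probability presented to the SRC would still count the patient as a complete non-DLT.
- **Recruitment has stopped.** Section 2.1 says so, and this sharply limits what can still go wrong.

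**Conclusion.** The inconsistency is real and narrow. It arises only when the Cycle 1 Day 15 dose is late and the patient is still in the window when the rest of the cohort is complete. The gap is at most 7 to 8 days. A changed decision also needs a DLT within it. If that happens in a three-patient 200 mg cohort after 0/3 at 100 mg, the outcome moves from staying at 200 mg to permitting 400 mg.

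Four stronger readings are tempting but not supported:

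- **That a stated share of cohorts is affected.** The documents give neither a delay rate nor an enrolment pattern. Nor do 8 unseen days out of 14 mean that 57% of the risk is unseen: Section 2.3 describes neutrophil and platelet falls immediately after infusion.
- **That delayed patients are mostly those with toxicity.** Sections 4.1.4.4 and 6.1 list adverse events alongside concurrent disease, surgery and individual reasons, with no breakdown.
- **That a Grade 3 laboratory event late in Cycle 1 would be scored DLT-free.** Section 5.3.6.2 exempts certain Grade 3 laboratory abnormalities on recovery within a week. Until recovery is shown the exemption is not met, so a non-DLT score does not follow automatically.
- **That the reported result is biased.** The SAP's final analysis counts DLTs over the prolonged window.

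The exposure is in interim escalation decisions and is limited now that recruitment has stopped. The point still merits correction: the DLT count remains a primary endpoint, and it should be clear which window past updates should have used.

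**What to change.** Reconcile the passages by using one definition: completion of the MTD evaluation period, including any prolongation under Section 5.3.6.2, as in SAP 5.1. Apply it in four places:

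1. the BLRM update trigger in Section 3.1;
2. the first evaluability criterion in Section 3.1;
3. the two-patient escalation rule in Section 3.1;
4. the review timing in Section 2.3.

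Add that a patient still inside the window at a planned update is pending and is not entered as DLT-free. State whether the dose day counts as day 1 of the 14, which removes the one-day ambiguity.

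The cost is protocol wording, plus a wait of up to about 8 days for the update in cohorts where the Day 15 dose was late. Cohorts dosed on schedule are essentially unaffected.
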